Incidence of drug discontinuation: Survival analysis will be undertaken to calculate the incidence rate of drug discontinuation (95% confidence intervals (CI)) per 1,000 personyears for entire study period, first 12-months of follow-up, and the subsequent period. Life tables will be constructed to estimate the cumulative incidence at 1-year and 5-year follow-up. Cumulative hazards will be plotted using Nelson-Aalen graphs. Data management and analysis will be performed in Stata MP v16.

Plan for addressing confounding

Bias due to transferring GP surgeries: To minimise bias due to prevalent users appearing as incident users in a new GP surgery, data for participants who receive a prescription of a DMARD within one year of their current registration in a GP surgery will be excluded from the cohort. This will minimise the chance of prevalent long-term users of these medicines entering the cohort as new incident-users.

Plans for addressing missing data

Multiple imputation using chained equations will be used to deal with missing data. We expect BMI, alcohol intake, smoking and ethnicity to have missing values. The number of imputations will depend on the extent of the missing data.

Missing data on blood test results: The CPRD has data about blood test results. However, it is possible that in some instances of drug discontinuation due to abnormal monitoring blood test results, the numerical blood test results are not available in the CPRD. However, just as

for other clinical events, the occurrence of abnormal blood tests is recorded using Read codes such as R144.11 (kidney function test abnormal), KO4..12 to KOE.0 (acute kidney injury) etc.; R148.00 and 44D2.00, 44G2.00 etc. (liver function test abnormal or abnormal liver enzymes); and D400.12 and 42J2.00 etc. (neutropenia) and D400600 and D400211 etc. (drug induced neutropenia); D315.00 D313z00 and 42P2.00 (thrombocytopenia). To reduce the risk of missing data, we will use either numerical blood test results or Read codes to define the outcome of interest. To minimise the risk of bias from missing data, participants with only one full blood count, liver function test and renal function test in the first year of drug prescription in primary care will be excluded from analysis. Similar steps will be taken in CPRD Aurum where applicable. For example, cleansedreadcode which define the occurrence of abnormal blood tests such as 44J3000 (serum creatinine abnormal), KO4..00 (acute renal failure); R148.11 (LFT's abnormal) and 44D2.00 (liver function test abnormal); and 42J2.00 (Neutropenia), 42J4.00 (Neutrophil count abnormal); 42H2.11 (Leucopenia) and 42P2.00 (thrombocytopenia) will be used in instances of missing numerical blood test results in Aurum.

Patient or user group involvement

The PPI panel will review and feedback on the performance of risk scores, with information presented in a way that is accessible to lay members. The risk prediction calculation will be applied to hypothetical case scenarios and the results presented to the PPI members to gauge initial acceptability. They will also comment on the net risk and net benefit from different monitoring strategies compared to no testing or testing all. Plans for disseminating and communicating study results

The results of this study will be presented at speciality and primary-care scientific meetings. They will be published in open access peer-reviewed journals. We will disseminate the findings to the wider medical community through publication in newsletters such as Pulse, and emails to the entire memberships of the British Societies for Rheumatology, Dermatology, Gastroenterology, Hepatology, Nephrology, Haematology, Pharmacology, Geriatrics, Royal College of Physicians, and the Royal College of General Practitioners. We will also disseminate the results to the National Patient Safety Agency as they are a key stakeholder. We will engage with Rheumatology, Dermatology, General-Practice, and Gastroenterology guideline writing groups to bring about a change in their national guidelines. Several coinvestigators already have strong links with these guideline writing groups. We will engage with MHRA and drug manufacturing authorisation holders to edit relevant monitoring recommendations in the British National Formulary, and, summary of product characteristics respectively. We will lobby NICE to see if an overarching monitoring guideline can be produced. We will also disseminate the findings directly to patient groups. We will work with Versus Arthritis, Arthritis and Musculoskeletal Alliance (ARMA), Crohn's and Colitis UK, British Skin Foundation and Psoriasis Association to disseminate the results to people with these conditions. As above several co-investigators have links with these patient societies. We will also publicise the study results directly to patients, through existing networks such as social media and Twitter accounts to maximise impact. We will be supported by the East Midlands AHSN, Versus Arthritis Pain Centre, and Nottingham NIHR-BRC in this endeavour. Finally, we will engage with traditional media, such as radio, TV, and newspapers to disseminate our study findings. The PPI volunteers will advise on the content of all public facing content for Dissemination.

Conflict of interest statement

None.

Limitations of the study design, data sources, and analytic methods Limitation of data source:

[1] Lack of information about biologic prescriptions in the CPRD: Biological agents (such as anti-TNF agents) are prescribed exclusively by hospital specialists, and this information is not recorded in the CPRD. Thus, it is possible that some individuals who discontinue non-biologic immune-suppressing treatment with a preceding abnormal blood test result, actually had an adverse drug reaction to the biological agent and the treating physician discontinued both treatments as a precaution. This will result in a higher rate of outcome i.e. drug discontinuation with a preceding blood test abnormality than the true outcome rate. Although not ideal, this is better than a bias in the opposite direction, as the results of our study have important patient safety implications.

[2] Drug discontinuation without any data for monitoring blood test results in the period of interest: It is possible that in some instances of drug discontinuations due to abnormal monitoring blood test results, the data for monitoring results are not available in the CPRD, in either the clinical or the observation files as Read codes and as numeric values respectively. This will reduce the annual rate of outcome of interest.

[3] There is a possibility that people at a very high risk of drug-toxicity, e.g. due to preexisting chronic liver or renal disease, or cytopenia due to bone marrow or peripheral consumption, may be prescribed immune-suppressing therapies directly by the hospital specialist, and these prescription details will not be available in the CPRD. Thus, our sample may be biased towards participants at a lower risk of side-effects. However, it is very rare to prescribed potentially hepatotoxic, nephrotoxic and myelotoxic drugs to patients with such serious illnesses and, our results will maintain broad generalisability.

[4] It is possible that for some patients on long-term methotrexate, the decision to discontinue therapy is based on non-invasive tests of fibrosis such as transient elastography. This would be a confounder and may increase the discontinuation in a later phase of treatment i.e. after 2 years, but, not due to abnormal liver enzymes. Data on transient elastography are included in hospital clinic letters and not available in the CPRD as a test result value. This would be a limitation to the risk prediction model.

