Question: What is the optimum strategy of blood testing after the first six months of primary-care immune-suppressing drug prescription?

Objectives: [1] Develop and validate a prediction model for estimating an individual's risk of target-organ damage conditional on their values of multiple prognostic factors available at 6 months of primary-care immune-suppressing drug prescription, [2] Identify incidence of drug discontinuation for any reason, and due to abnormal monitoring blood test results in each year of prescription.

Methods: Data from Clinical Practice Research Datalink (CPRD) Gold and Aurum will be used. We will utilise CPRD-HES linked data to validate the sensitivity of outcome definition in primary-care data alone.

People with common inflammatory conditions treated with immune-suppressing drugs, will be followed up electronically from day 180 of the first primary-care prescription of a drug of interest until the earliest of target-organ adverse event, drug discontinuation, death, moving to a different practice, 5-year follow-up time, or 31/12/2019 (study end date).

A penalized flexible parametric survival model will be used to develop a risk prediction score for drug discontinuation due to target organ damage using CPRD Aurum given its larger sample size, accounting for competing risks as necessary, and with internal validation using bootstrapping to quantify and adjust for optimism. The predictive performance of the score will be validated in CPRD Gold. GP practices contributing data to both CPRD Aurum and GOLD will be excluded from the validation cohort. Separate risk scores will be developed and validated for each drug of interest. Risk thresholds will be agreed using decision curve analysis and with patient and clinician involvement. Incidence (per 1,000 person-years) of treatment discontinuation in each 12-month of primary-care prescription will be estimated.

Outcomes to be measured

Primary outcome: Drug discontinuation due to target organ specific adverse event. This will be defined as drug discontinuation with either (a) abnormal blood test results due to target-organ damage, or (b) target organ damage based on clinical code allocation.

Drug discontinuation due to abnormal monitoring blood test results will be defined as present when there is:

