[2] Identify incidence of drug discontinuation due to any reason and due to abnormal monitoring blood test results in each year of prescription.

Synergy with ongoing research: We have an ISAC approved study (reference number 19_275R) developing a risk-prediction score for liver, blood or kidney damage from methotrexate and leflunomide in people with auto-immune rheumatic diseases, using data from the Clinical Practice Research Datalink (CPRD).

We are seeking approval for additional work to [1] conduct prediction modelling for azathioprine, sulfasalazine, aminosalicylates (such as mesalazine), and mycophenolate, and [2] expand analysis of methotrexate to include patients with psoriasis (without psoriatic arthritis) and inflammatory bowel disease.

Leflunomide is only licenced for the treatment of RA and psoriatic arthritis and we do not propose to expand the modelling to other common inflammatory conditions for this drug for this reasons.

We can confirm that these analyses were not included in our previously approved application.

Study background

A. What is the problem being addressed?

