Cohort entry and start of follow-up: At first prescription and day 180 of the first primarycare prescription of a drug of interest respectively. Separate cohorts will be built for each drug.

Cohort exit: Earliest of target-organ adverse event, drug discontinuation, death, moving to a different practice, 5-year follow-up time, or 31/12/2019 (study end date).

Inclusion criteria:

[1] Diagnosis of any common inflammatory disease i.e. RA, inflammatory bowel disease, psoriasis +/- arthritis, ankylosing spondylitis, systemic lupus erythematosus, or reactive arthritis. These are the commonest inflammatory conditions treated with immune-suppressive drugs.

[2] Age ≥18 years at diagnosis.

[3] At least one GP prescription of methotrexate, azathioprine (or mercaptopurine), aminosalicylates, sulfasalazine, mycophenolate. These are the most commonly prescribed immune-suppressing drugs for which blood test monitoring is recommended.
[4] Meeting CPRD data quality standards (UTS for Gold and acceptable flag for Aurum) and with a continuous registration for at least one year before the first date of diagnosis of inflammatory disease in CPRD Gold and CPRD Aurum.

The requirement to have one-year disease free registration in the CPRD prior to first date of inflammatory disease diagnosis is to allow for the identification of incident cases, and those newly commenced on immune-suppressing drugs. This will exclude prevalent cases of inflammatory diseases on long-term hospital prescribed immune-suppressive drugs who have recently switched to GP prescription due to implementation of primary-care/secondary-care shared care prescribing in their area.

Exclusion criteria: Presence of any of the below prior to cohort entry:

[1] eGFR < 15 ml/min or chronic kidney disease stage 4 or 5.

[2] Chronic liver disease: Autoimmune hepatitis, hepatitis B or C, cirrhosis

[3] Pre-existing hematological abnormalities: Myelodysplasia, primary hematological diseases causing neutropenia or thrombocytopenia.

[4] Prescription of the immunosuppressive drugs listed above before first inflammatory disease diagnosis date.

[5] Registered in GP practices not meeting CPRD data quality standard at cohort entry.

Selection of comparison group(s) or controls

A comparison group is not applicable in the context of risk prediction modelling. Exposures, outcomes and covariates

Predictors of drug discontinuation: Candidate prognostic factors will be identified using two approaches:

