[1] Theory driven based on prior knowledge: A list of recognised prognostic factors for abnormal monitoring blood test results have been developed based on the research teams' clinical experience. The a priori agreed prognostic factors include: age, sex, body mass index, alcohol consumption, smoking, CKD stage 3, type 2 diabetes, and prescription of selected drugs that increase risk of acute kidney injury or transaminase elevation at baseline.

[2] Evidence based, based on systematic review: A systematic review of existing literature is currently underway to identify other prognostic factors. This will provide additional candidate predictors (PROSPERO: CRD42020208049).

The presence of comorbid and lifestyle prognostic factors will be ascertained using primarycare diagnoses and lifestyle data collected in the two-years preceding cohort entry. The presence of prescription prognostic factors will be ascertained using primary-care prescriptions in the 180 days preceding cohort entry.

Outcomes

Primary outcome: Target organ specific adverse event resulting in drug discontinuation from 6 months of initial primary-care prescription to until 5-years after the initial prescription.

This will be defined as drug discontinuation with either (a) diagnosed with target organ damage based on clinical code, or (b) significant abnormal blood test results.

Drug discontinuation due to abnormal monitoring blood test results will be defined as present when there is:

(a) a gap between two prescriptions, or between last prescription date and earliest of death date, moving to a different practice, 5-year follow-up time, or 31/12/2019 (study end date) of \geq 90 days, and

(b) an abnormal blood-test result in the 15 days preceding or 45 days after the last prescription date. The 15-day preceding window is to allow for any delay in acting on abnormal blood-test results.

Abnormal blood test results will be defined according to the British Society for Rheumatology DMARD monitoring guidelines 1, and CKD progression will be defined as per the Kidney Disease Improving Global Outcomes guideline 20122:

- White blood cells <3.5x109/L,
- Neutrophils <1.6x109/L,
- Platelets <140x109/L,
- Alanine Transaminase and/or Aspartate Transaminase >100 units/L,

• CKD progression defined as creatinine difference > 26 micro mol/L above the first or second preceding result or chronic kidney disease stage progression.

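### The incidence analysis uses intervals and a time origin that do not match the yearly rates promised in objective 2

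*Protocol*

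**What the plan says.** Under Objectives, specific aims and rationale, the second objective of the Protocol is: "Identify incidence of drug discontinuation due to any reason and due to abnormal monitoring blood test results in each year of prescription". The Methods paragraph of the Technical summary agrees with it: "Incidence (per 1,000 person-years) of treatment discontinuation in each 12-month of primary-care prescription will be estimated".

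The paragraph on incidence of drug discontinuation, under Data/statistical analysis, is the only place where the calculation is set out. It specifies rates per 1,000 person-years with 95% confidence intervals "for entire study period, first 12-months of follow-up, and the subsequent period". It adds two outputs: "Life tables will be constructed to estimate the cumulative incidence at 1-year and 5-year follow-up", and "Cumulative hazards will be plotted using Nelson-Aalen graphs". It speaks of drug discontinuation in general and does not name the two types listed in the objective.

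The study population section separates cohort entry from the start of follow-up: "At first prescription and day 180 of the first primarycare prescription of a drug of interest respectively". The primary outcome is counted "from 6 months of initial primary-care prescription to until 5-years after the initial prescription".

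**The concern.** The objective and the analysis section differ in two ways. The first is the intervals: one side promises a rate for each year, the other gives an overall rate and a two-way split. The second is the clock: the objective counts years of prescription, while the analysis counts follow-up, which starts about half a year later. An analyst who follows the analysis section literally will not produce what the objective names. Two analysts could report different tables, each with support in the Protocol.

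What is at stake is the descriptive evidence on how discontinuation changes with time on the drug. The background argues that the yield of monitoring falls as treatment continues, and the stated purpose is to inform how often to test. Yearly rates are the plainest way to show whether, and in which year, discontinuation for abnormal tests declines. A single rate for all time after month 18 cannot show that.

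**Working it through.** The Protocol gives no figure for this analysis that could be reproduced, so the check maps one clock onto the other.

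**Inputs from the Protocol.** Cohort entry is at first primary-care prescription (day 0). Follow-up starts at day 180. The rate windows are the first 12 months of follow-up and the time after that. Prescription years are taken as 365 days, so anniversaries fall at days 365, 730, 1,095, 1,460 and 1,825.

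**First window.** It runs from day 180 to day 180 + 365 = 545.
- In prescription year 1: 365 − 180 = 185 days.
- In prescription year 2: 545 − 365 = 180 days.

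It is an almost equal mixture of two prescription years.

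**Subsequent window.** It starts at day 545, which is 545/365 × 12 ≈ 17.9 months of prescription.
- If observation ends 5 years after first prescription, it runs to day 1,825. That is 1,280 days: 185 of year 2 and 365 each of years 3, 4 and 5.
- If the 5 years run from day 180, it ends at day 2,005 and adds 180 days of year 6. The primary outcome definition supports the first reading. The cohort exit rule, which refers to 5-year follow-up time, leaves the second open.

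On either reading, neither window is a prescription year.

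**What the two windows return.** The yearly rates below are assumptions for illustration, per 1,000 person-years, with observation ending at day 1,825. The simple formula weights each year's rate by its days in the window.

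Assumed rates 40, 25, 20, 15, 10 for years 1 to 5:
- First window: (185 × 40 + 180 × 25)/365 = 11,900/365 = 32.6.
- Subsequent: (185 × 25 + 365 × 20 + 365 × 15 + 365 × 10)/1,280 = 21,050/1,280 = 16.4.

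Weighting each day by the fraction still on the drug changes these slightly:

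| Assumed rates, years 1–5 | First 12 months of follow-up | Subsequent period |
|---|---|---|
| 40, 25, 20, 15, 10 | 32.7 | 16.5 |
| 60, 20, 15, 10, 10 | 40.5 | 12.9 |
| 20 throughout | 20.0 | 20.0 |

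Two numbers cannot determine five yearly rates. They equal the yearly rates only when the hazard is constant. Splitting the same follow-up at the anniversaries returned the assumed yearly rates exactly in all three cases, with year 1 contributing only its second half (about 0.5 person-years per person, against 0.92 to 0.98 in each later year).

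**The other outputs.** Life-table estimates at 1 and 5 years of follow-up fall at day 545 and, with follow-up counted from day 180, day 2,005. Neither is a prescription anniversary, and nothing is reported between them. A Nelson-Aalen curve covers all follow-up, and its slope shows where the hazard changes, but it does not give a rate and confidence interval for each year.

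**The case against.** The best defence is that the Protocol does contain a plan for yearly rates: the Technical summary states it under Methods, in line with the objective. The analysis section also offers more than two rates, since the cumulative hazard plot would show a falling hazard to anyone who reads its slope. Both points stand. A reader might infer that objective 2 has no analysis or cannot be answered, and the documents do not support that. The planned data can be split by year from day 180 onward, and one part of the text says they will be. What the defence does not remove is that the detailed section specifies something else, on another clock.

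A reader might also infer that leaving out days 0 to 179 is an error that hides the highest-risk period. The documents do not support this either. The research question and overall purpose are restricted to the time after six months of primary-care prescription, so the late start is deliberate. The background places most side-effects in the first six months after treatment starts in hospital, with handover to the GP just after the target dose is reached at three to four months. On that pathway, much of the high-risk period precedes the first GP prescription.

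Nor is counting events from day 0 clearly sound. Under the plans for missing data, people with only one set of blood tests in the first year of primary-care prescription are excluded. Those who stop early have less time to accumulate repeat tests, so a rate for days 0 to 179 could be biased downward.

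**Conclusion.** The point holds as an internal inconsistency. The rates specified under Data/statistical analysis do not deliver the yearly rates promised by objective 2 and the Technical summary, because both the intervals and the time origin differ. The first window mixes 185 days of prescription year 1 with 180 days of year 2, and everything after about month 18 becomes one rate. The day mapping rests only on the Protocol's own definitions and 365-day years. The distortion of the rates depends on the assumed yearly hazards: it is nil if the hazard is constant and grows with the steepness of the decline, which is the pattern the background expects.

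The consequence is limited. Objective 2 is descriptive, the data needed are already in the plan, and the prediction model does not use these rates.

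**What to change.** Amend the incidence paragraph under Data/statistical analysis so that it agrees with objective 2 and the Technical summary:

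- Split follow-up at prescription anniversaries and report rates per 1,000 person-years with 95% CI for each prescription year up to year 5.
- Report these separately for discontinuation for any reason and for discontinuation due to abnormal monitoring blood tests.
- State that time is counted from first primary-care prescription with entry into the risk set at day 180, so that year 1 covers days 180 to 365 only, and label it so in the tables.
- State whether the 5-year limit runs from first prescription or from day 180.

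The overall rate, life tables and Nelson-Aalen plots can stay. The cost is a few lines of Protocol text and one time split of data already planned for extraction. The downside is wider confidence intervals for the later years, since the pooled period is divided into four pieces.

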Sample size for prediction modelling should aim to minimise overfitting and estimate key parameters precisely. This is the premise of Riley et al [34] sample size criteria. Assuming a mean follow-up of 1 year and a rate of 0.02 per person year such that at 6 months outcome risk is 1%, then the max R squared is 0.18. Conservatively assuming that 15% of variation is explained by our model (model R squared is 0.027), then with 50 candidate predictor parameters, the criteria of Riley et al [34] suggests 6.57 events per parameter, therefore 329 outcome events are required, and 16,416 participants are needed for developing the prognostic model.

We will use data from CPRD Aurum to develop the prognostic model for mesalazine, sulfasalazine, azathioprine, and mycophenolate. We are reasonably confident that there will be sufficient sample size to develop a prognostic model for all drugs of interest with the exception of mycophenolate.

Our ongoing ISAC approved study (ISAC reference number 19_275R) has used data from CPRD Gold to develop a prognostic model for methotrexate toxicity in patients with autoimmune rheumatic diseases, and is validating it using data from the CPRD Aurum. To maintain synchrony with ongoing research we will include data for patients with psoriasis and inflammatory bowel diseases treated with methotrexate in CPRD Gold database in the model development dataset and from CPRD Aurum database when validating prognostic model for methotrexate toxicity.

Planned use of linked data and/or withheld concepts HES admitted patient care:

We anticipate that serious blood, liver or renal organ system drug toxicities may lead to hospitalisation and these outcome events may not be ascertained using primary care

dataset alone if the abnormal blood-test result is not recorded in primary care. However, our clinical experience suggests that such outcomes are very rare. Due to sample size limitations (as 68.5% and 65.7% of CPRD Gold and Aurum respectively have linkage to HES), an analysis restricted to CPRD-HES linked data is not appropriate, as a third of sample-size will be lost with only a few outcome events gained. Therefore, a sample will be drawn from the study population with HES linkages to validate the sensitivity of outcome definition using primary-care data alone.

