The theory driven and systematic review derived prognostic factors will be included in a flexible parametric survival model, to identify the prognostic factors (predictors) of the outcomes of interest i.e. target organ specific adverse events or drug discontinuation due to abnormal monitoring blood test results. Multiple imputation using chained equations will be used to deal with missing data. The number of imputations will depend on the extent of missing data. All of the data available in the CPRD Aurum (except for methotrexate where we will continue to use CPRD Gold for model development) will be used to develop the risk prediction model. All candidate predictors will be included. We will form the risk equation for the outcome of interest by a function of the estimated β coefficients multiplied by values of the corresponding predictors included in our model together with the baseline hazard function. This process ultimately leads to an equation for the predicted absolute risk over time. We will examine the performance of this final model in terms of discrimination by calculating the c-statistic and calibration by plotting agreement between predicted and observed risks across the whole range of predicted risk at relevant time-points (calibration plot with smoothed calibration curves, with measures of calibration-in-the-large and calibration slope, as estimated using pseudo-observations). As part of the process of internal validation, to account for optimism caused by over-fitting, for each imputation separately, we will develop a model separately within 100 samples of the derivation data with replacement of the same size of the original sample (bootstrap samples). From this the optimism will be estimated by comparing the performance of the model in the bootstrap samples with the same model in the original sample. We will then estimate the overall optimism averaged over all 100 models in each imputed dataset and estimate a uniform shrinkage factor, equal to the average of the calibration slopes from each of the bootstrap samples. The process will be repeated for each imputed dataset, and the final uniform shrinkage calculated by averaging across the estimated shrinkage estimates from the imputations. Then, to account for over-fitting during the development process, we will multiply (penalize) the original β coefficients by the uniform shrinkage factor. At this point, the baseline hazard will be re-estimated on the basis of the shrunken β coefficients to ensure that overall calibration is maintained, producing a final model. Outcomes affected by competing events (e.g. discontinuation due to renal or liver abnormalities) will be accounted for using a competing risks and multi-stage modelling framework, within the flexible parametric framework via a subdistribution (Fine and Gray) approach [38]. Continuous predictors will not be categorised and potential non-linear effects examined using fractional polynomials.

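### Life tables with no competing-risk provision would overstate the 5-year cumulative incidence of discontinuation due to abnormal blood tests

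*Protocol*

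**What the plan says.** The second objective in the Protocol (Objectives, specific aims and rationale) is: "Identify incidence of drug discontinuation due to any reason and due to abnormal monitoring blood test results in each year of prescription". It therefore covers two outcomes, one of which is specific to a cause.

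Under Data/statistical analysis, the paragraph on incidence of drug discontinuation plans rates per 1,000 person-years and then two further summaries: "Life tables will be constructed to estimate the cumulative incidence at 1-year and 5-year follow-up" and "Cumulative hazards will be plotted using Nelson-Aalen graphs". It does not mention competing events.

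The study population section sets what ends follow-up: "Cohort exit: Earliest of target-organ adverse event, drug discontinuation, death, moving to a different practice, 5-year follow-up time, or 31/12/2019 (study end date".

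Competing risks are addressed for the risk score only. The technical summary allows for them where necessary. The section on deriving and validating the prediction model says "Outcomes affected by competing events (e.g. discontinuation due to renal or liver abnormalities) will be accounted for using a competing risks" and places this "within the flexible parametric framework via a subdistribution (Fine and Gray) approach". Neither statement reaches the life tables.

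**The concern.** Under the exit rule, a patient who stops the drug for another reason, or who dies, leaves the cohort and cannot later be counted as stopping because of an abnormal test. For that outcome these exits are competing events. A standard life table for one cause treats them as withdrawals. Its complement is then the risk in a hypothetical setting where nobody stops for another reason and nobody dies. That is never below the cumulative incidence, and it exceeds it as soon as competing events occur. The Protocol names cumulative incidence as the target, so for this outcome the named quantity and the named method do not match.

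At stake is a descriptive figure: the proportion of patients who, in practice, stop because of an abnormal test within 1 and 5 years. The study would also report absolute risks from a subdistribution model for the closely related primary outcome. The two sets of figures would estimate different quantities and would not agree.

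**Working it through.** **Inputs**
- Outcome rate h1 = 0.02 per person-year, from Sample size considerations: "Assuming a mean follow-up of 1 year and a rate of 0.02 per person year". It is a planning value, used here as the hazard of abnormal-test discontinuation.
- Competing hazard h2 (stopping for another reason, plus death): not given in the Protocol. Assumed 0.05 to 0.20 per person-year, with 0.02 and 0.30 as outer values.
- Both hazards are taken as constant.

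**The plan's own figures.** The Protocol states no 1-year or 5-year cumulative incidence, so there is none to reproduce. The 0.02 rate can be checked in use:
- 6-month risk: 1 − exp(−0.02 × 0.5) = 0.00995, the stated 1%.
- Sample size "with 50 candidate predictor parameters", model R² 0.027 and a shrinkage target of 0.9 (assumed; not stated): 50 / [(0.9 − 1) × ln(1 − 0.027/0.9)] = 16,415.4, against the stated 16,416. Events: 16,415.4 × 0.02 = 328.3, against 329.

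**Formulas**
- Life table with competing exits treated as withdrawals: 1 − exp(−h1·t).
- Cumulative incidence: h1/(h1 + h2) × [1 − exp(−(h1 + h2)·t)].

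**Example, h2 = 0.10, t = 5**
- Life table: 1 − exp(−0.10) = 0.0952.
- Cumulative incidence: 0.02/0.12 × [1 − exp(−0.60)] = 0.1667 × 0.4512 = 0.0752.

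**Results** (gaps in percentage points, from unrounded values)

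| h2 per person-year | Life table, 5 y | Cumulative incidence, 5 y | Gap, 5 y | Ratio, 5 y | Gap, 1 y |
|---|---|---|---|---|---|
| 0.02 | 9.52% | 9.06% | 0.45 | 1.05 | 0.02 |
| 0.05 | 9.52% | 8.44% | 1.08 | 1.13 | 0.05 |
| 0.10 | 9.52% | 7.52% | 2.00 | 1.27 | 0.10 |
| 0.20 | 9.52% | 6.06% | 3.45 | 1.57 | 0.18 |
| 0.30 | 9.52% | 4.99% | 4.53 | 1.91 | 0.27 |

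**Checks**
- A simulated actuarial life table with annual intervals and administrative censoring gave 9.54%, 9.46% and 9.41% for h2 = 0.05, 0.10 and 0.20. The closed form is therefore a fair guide to what the planned method would print.
- If the 5-year limit is counted from the first prescription, follow-up from day 180 is about 4.5 years. The gap for h2 = 0.05 to 0.20 is then 0.89 to 2.89 points.
- The ratio hardly depends on h1. At h2 = 0.10 and 5 years it is 1.27 for h1 = 0.01 and 1.26 for h1 = 0.04.

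**Any-reason discontinuation.** Stops for other reasons are now events, and only death competes. The same formulas apply with a smaller h2, so the ratio lies closer to 1. The Protocol gives no death rate, so no figure is attached.

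**The case against.** The best case for the plan is that it never says it will do this. The incidence paragraph refers only to drug discontinuation, and the secondary outcome is discontinuation for any reason. If the tables serve only that outcome, other-reason stops are events and the figures above do not apply. The paragraph does not mention censoring either; that follows from the exit rule and from how a standard life table works. Objective 2 asks for incidence in each year of prescription, which the person-year rates supply, and those are valid cause-specific rates. The competing hazard is assumed.

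Much of this stands, and it is why the point is conditional on the tables serving the abnormal-test outcome. It does not remove the point. Objective 2 names that outcome, the incidence paragraph is the only analysis written for that objective, and it names an estimator for cumulative incidence. The wrong estimator for one of the two outcomes is more than detail left to an analysis plan.

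Three stronger readings are tempting, and the Protocol does not support them:
- A reader might infer that comparisons between drugs would be distorted. None is planned: cohorts and scores are built separately for each drug.
- A reader might infer that the prediction model ignores death and stopping for other reasons, because its only example is renal or liver discontinuation. That example is illustrative, and the subdistribution approach leaves room for both.
- A reader might take the 57% relative excess at h2 = 0.20 as the expected error. It is the top of an assumed range.

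**Conclusion.** The point holds in conditional form. If the life tables are used for discontinuation due to abnormal tests, their complement overstates the cumulative incidence. The direction is certain; the size is not. With 0.02 per person-year and constant hazards, the 5-year figure is 1.1 to 3.5 points too high for an assumed competing hazard of 0.05 to 0.20 per person-year, and the 1-year figure is less than 0.2 points too high over the same range. As a yardstick, the Protocol aims for a 99% margin of ±0.55 points on the simple proportion stopping for abnormal tests, so across this range the 5-year bias would exceed that margin. For any-reason discontinuation the bias should be smaller, in relative terms.

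The rates per 1,000 person-years, the risk score and its absolute risks do not depend on the life tables and are unaffected. The change is worth making before analysis, but it concerns a descriptive result and not the study's main product.

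**What to change.** In the paragraph on incidence of drug discontinuation:
- State which outcomes the 1-year and 5-year figures cover.
- For discontinuation due to abnormal tests, replace the life table with the Aalen-Johansen estimator, with discontinuation for other reasons and death as competing events.
- For any-reason discontinuation, use the same estimator with death as the competing event.

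The person-year rates can stay as planned. The Nelson-Aalen plots can stay as displays of cumulative hazard, provided they are not read as risks.

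The cost is about two sentences of text and one changed command. It needs no further data. The downside is that the reported cumulative incidences become slightly lower.
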